2.4.4 Antithrombotic Therapy

Antithrombotic therapy throughout the study should consist of a vitamin K antagonist (e.g. warfarin, fluindione, phenprocoumon, etc.) and the treatment arm medication. No additional anti-platelet agents

Clinical Investigation Plan

will be added while patients are on the treatment arm medication. The treatment arm medication will be taken once daily by mouth. Vitamin K antagonist therapy will be per standard of care (SOC) with a target INR of 2.0-3.0. The use of aspirin and a vitamin K antagonist is normal clinical practice at many centers and is part of the HM3 IFU.

2.4.5 Treatment Arm Medication Accountability

To ensure treatment arm medication accountability, all bottles including (if applicable) all unused doses will be returned to ALMAC Clinical Services by the site. Subjects will be instructed to return the bottle and any unused doses of the treatment arm medication at each resupply visit.

The bottles and unused doses will be shipped (at the Sponsor's expense) per country- or region-specific Treatment Arm Medication Accountability Return Instructions.

In the event that a site has several bottles or unused portions to return to ALMAC Clinical Services, return shipments may be combined into a batch shipment. Empty research bottles and unused doses should not be stored on site and should be shipped to ALMAC Clinical Services within 14 days of receipt from the subject. Treatment Arm Medication Accountability Return Instructions will be provided during training.

2.4.6 Aspirin Response Testing

NOTE: Additional antiplatelet testing or platelet function testing, beyond the core lab test, should not be performed while patients are on the treatment arm medication, as it may result in un-blinding of the subject or the investigator.

3.0 CLINICAL INVESTIGATION DESIGN

This is a prospective, randomized, double-blinded, placebo-controlled clinical investigation of advanced heart failure patients treated with the HM3 with two different antithrombotic regimens: vitamin K antagonist with aspirin versus vitamin K antagonist with placebo. Subjects will be randomized in a 1:1 ratio.

Clinical Investigation Plan

The clinical investigation has been designed to involve as little pain, discomfort, fear, and any other foreseeable risk as possible for subjects. Refer to the Risks Analysis section of the clinical investigation plan for details.

The clinical investigation will be conducted at up to 50 centers worldwide. Greater than 50% of the patients enrolled in this study will be from centers based in the United States. The primary and secondary endpoints will be evaluated according to the statistical section (Section 8 and in the study statistical analysis plan; SAP). Outcomes for this study include death, transplant, withdrawal or pump exchange. All subjects, site, Clinical Events Committee (CEC), and sponsor personnel will remain blinded to the randomization scheme until the last ongoing study subject completes follow-up (specifically, experiences an outcome or has final study visit) and all data have been collected and adjudicated. Exceptions will be justified in the study blinding plan (e.g. DSMB). After a patient reaches 12-months of follow up, they will continue to be followed every 6-months, as long as they remain on the treatment arm medication, until the last ongoing patient reaches 12-months of follow up. Beginning at the 12-month follow-up visit, patients should be requisitioned two bottles of the treatment arm medication to cover the 6 months until the next follow up visit.

3.1 Clinical Investigation Procedures and Follow-up Schedule

The study flow chart (Figure 2) and the follow-up schedule of this clinical investigation are described below.

Clinical Investigation Plan

[figure not shown]

Figure 2 – Clinical Investigation Flow Chart

Clinical Investigation Plan

3.2 Measures Taken to Avoid and Minimize Bias

This study is designed to minimize bias by blinding all subjects, site personnel, sponsor personnel, and the CEC to the randomly assigned treatment regimen. Furthermore, screening logs will be captured including details on patients who are excluded from the study only because of investigator mandated antiplatelet therapy (presence or absence) prior to or after consent to understand any effect of selection bias on the generalizability of the study.

3.3 Suspension or Early Termination of the Clinical Investigation

While no formal statistical rule for early termination of the clinical investigation for insufficient effectiveness of the device under investigation is defined by the Sponsor or Steering Committee, the Sponsor reserves the right to discontinue the clinical investigation at any stage or reduce the follow-up period with suitable written notice to the investigator. Possible reason(s) may include, but are not limited to:

- Unanticipated adverse device effect (e.g., UADE) occurs and it presents an unreasonable risk to the participating subjects
- An oversight committee (e.g., Steering Committee, DSMB) makes a recommendation to stop or terminate the clinical investigation (such as in the event of higher frequency of anticipated adverse device effects)
 - The Data Safety Monitoring Board will create independent rules for study oversight including prespecified rules for recommending cessation of the study, which will be captured in the DSMB charter. In the event these rules are met, the sponsor will meet with the Steering Committee. The Sponsor will notify sites and, if agreed with the Steering Committee, enrollment in the study will be paused.
- Further study progress is cancelled.

Should the clinical investigation be discontinued by the Sponsor, subjects will be followed per routine hospital practice with device-related AEs reported to the Sponsor as per vigilance/commercial reporting requirements. The investigator shall return all clinical investigation materials (including both partially used and unused treatment arm medication bottles) to ALMAC or the Sponsor, as appropriate, and provide a written statement to the IRB/EC (if applicable). All applicable clinical investigation documents shall be subject to the same retention policy as detailed in Section 11.5 of the CIP.

A Principal Investigator, IRB/EC or regulatory authority may suspend or prematurely terminate participation in the clinical investigation at the investigational site(s) for which they are responsible. The investigators will follow the requirements specified in the Clinical Trial Agreement.

If the Sponsor suspends or prematurely terminates the clinical investigation at an individual site in the interest of safety, the Sponsor will inform all other Principal Investigators.

If suspension or premature termination occurs, the Sponsor will remain responsible for providing resources to fulfill the obligations from the CIP and existing agreements for following the subjects enrolled in the clinical investigation, and the Principal Investigator or authorized designee will promptly inform the enrolled subjects at his/her site, and return patients to their standard medical treatment.

Clinical Investigation Plan

4.0 ENDPOINTS

4.1 Primary Endpoint and Rationale

The primary endpoint for this study will be met if the placebo arm is non-inferior to the aspirin arm in the composite of survival free of any non-surgical¹ major hemocompatibility related adverse event² at 1-year post implant.

¹ - Non-surgical is defined as any event occurring > 14-days post implant.

² - Major Hemocompatibility Related Adverse Events include:

- Stroke
- Pump Thrombosis (suspected or confirmed)
- Bleeding (including intracranial bleeds that do not meet the stroke definition)
- Arterial Peripheral Thromboembolism.

This study assesses the overall change in the overall incidence of major hemocompatibility related adverse events between the two groups. Additional secondary endpoints will also be evaluated to monitor effects on other safety and efficacy measures.

This composite primary endpoint reflects the interrelatedness of hemocompatibility related adverse events, providing an endpoint that will result in a clear answer to the study's primary question of whether or not anti-platelets are required to maintain the safety and efficacy profile of the HM3. Because the post-implant clinical course can be widely variable due to clinical responses to adverse events, this composite endpoint focuses on the first major hemocompatibility related adverse event to ensure the effect of the treatment arm is reflected in the primary endpoint measure. Non-composite endpoints or endpoints that do not focus on the first event have the possibility of being rendered futile or distorted by treatment responses to prior adverse events. Refer to section 8 of this CIP and the SAP for details.

4.2 Secondary Endpoint

As secondary endpoints:

- Non-surgical Major Hemorrhagic Events
- Non-surgical Major Thrombotic Events
- Survival
- Stroke Rates,
- Pump Thrombosis Rates
- Bleeding Rates, including:
 - Non-surgical Bleeding
 - Moderate Bleeding
 - Severe Bleeding
 - Fatal Bleeding
 - GI Bleeding

will be compared between the two arms of the study as detailed in section 8 of this CIP and the SAP.

Clinical Investigation Plan

4.3 Descriptive Endpoints

This study will also assess changes in the Hemocompatibility Score, Rehospitalization, and Economic Cost Implications as a result of removal of antiplatelet therapy from the antithrombotic regimen. Refer to section 8 of this CIP and the SAP for details.

5.0 SUBJECT SELECTION AND WITHDRAWAL

5.1 Subject Population

This clinical investigation will enroll male and female subjects from the advanced heart failure population who, as part of their standard course of treatment, will receive a HM3 LVAD. Subjects are considered enrolled when they provide written informed consent. Subjects must meet all applicable eligibility criteria and provide written informed consent prior to the conduct of any investigation-specific procedures not considered standard of care. Furthermore, patients must meet all randomization eligibility requirements at randomization. Only randomized subjects will continue to be followed in this study. Subjects not meeting randomization eligibility requirements will be considered screen failures and withdrawn from the study. Reason(s) for not meeting randomization eligibility requirements will be captured in the study EDC. Randomized subjects ongoing without a surgical adverse event, defined as ≤ 14 days post-implant, requiring investigator mandated antiplatelet therapy will form the analysis population for study endpoints. Details are available in section 8 of this CIP and the SAP.

5.2 Subject Screening and Informed Consent

5.2.1 Subject Screening

Patients receiving an LVAD at study sites should be considered for enrollment. All patients evaluated for inclusion in the clinical study, including those who provide informed consent and are enrolled, will be recorded on the site screening log. Rationale for exclusion from the trial will be recorded. Specifically, reasons may include refusal to consent, did not meet eligibility criteria or other specified reasons. To monitor for selection bias in enrollment, any patient excluded exclusively due to an investigator mandated antiplatelet therapy (either mandated antiplatelet presence or mandated absence of antiplatelets) will require specific clinical reasons recorded on the screening log.

Potential subjects presenting at the clinical sites will be fully informed about the clinical investigation, following the established informed consent process (described in Section 5.2.2). Once informed consent is obtained, subjects are considered enrolled. Thereafter, all subjects will have required baseline data beyond site standard of care captured and US-based patients will have blood drawn for baseline aspirin responsiveness testing (per section 2.4.6). Subjects who do not meet enrollment or randomization criteria will be considered screen failures.

5.2.2 Informed Consent

The Investigator or his/her authorized designee will conduct the informed consent process, as required by applicable regulations and the center's IRB/EC. This process will include a verbal discussion with the subject on all aspects of the clinical investigation that are relevant to the subject's decision to participate, such as details of clinical investigation procedures, anticipated benefits, and potential risks of clinical investigation participation. Subjects must be informed about their right to withdraw from the clinical

Clinical Investigation Plan

investigation at any time and for any reason without sanction, penalty or loss of benefits to which the subject is otherwise entitled. Withdrawal from the clinical investigation will not jeopardize their future medical care or relationship with the investigator.

During the discussion, the Principal Investigator or his/her authorized designee will avoid any improper influence on the subject and will respect the subject's legal rights. Financial incentives will not be given to the subject. The subject shall be provided with the informed consent form written in a language that is understandable to the subject and has been approved by the center's IRB/EC. The subject shall have adequate time to review, ask questions, and consider participation. The Principal Investigator or his/her authorized designee will make efforts to ensure that the subject understands the information provided. If the subject agrees to participate, the informed consent form must be signed and dated by the subject and thereafter by the person obtaining the consent prior to any clinical investigation-specific procedures beyond SOC. The signed original will be filed in the subject's hospital or research charts, and a copy will be provided to the subject.

Failure to obtain informed consent from a subject prior to clinical investigation enrollment should be reported to Sponsor within 5 working days and to the reviewing center's IRB/EC according to the IRB's/EC's reporting requirements.

If, during the clinical investigation, new information becomes available that can significantly affect a subject's future health and medical care, the Principal Investigator or his/her authorized designee will provide this information to the subject. If relevant, the subject will be asked to confirm their continuing informed consent in writing.

In addition, an authorization for use and disclosure of the subject's protected health information, in accordance with the Health Insurance Portability and Accountability Act (HIPAA) or local equivalent, as applicable, must be obtained from the subject. This may be incorporated into the main ICF or captured as a standalone document.

This study will not permit informed consent via legally authorized representatives. Therefore, incapacitated individuals, including the mentally handicapped or individuals without legal authority or individuals under the age of 18 or local age of legal consent, are excluded from the study population. Furthermore, individuals unable to read or write are excluded from the study population.

5.3 Eligibility Criteria

Assessment for general eligibility criteria is based on the medical records of the site and an interview with a candidate patient. If some of the clinical and laboratory tests are not included in site standard tests, they must be done but after written informed consent is obtained. Patients must meet ALL of the inclusion criteria to be considered for the clinical investigation. If ANY of the exclusion criteria are met, the patient is excluded from the clinical investigation and cannot be enrolled. If the subject is found after the time of informed consent but prior to randomization to no longer meet any of the inclusion criteria, or to meet any of the exclusion criteria (randomization eligibility), the subject will not be randomized and will be considered a screen failure and withdrawn from the study.

Clinical Investigation Plan

5.3.1 Inclusion Criteria

1. Subject will receive the HeartMate 3 per standard of care (SOC) in accordance with the approved indications for use in the country of implant.
2. Subject will receive the HeartMate 3 as their first durable VAD.
3. Subject must provide written informed consent prior to any clinical investigation related procedure.
4. In patients of child bearing capability, subject will not be currently pregnant or breastfeeding and on appropriate contraception.

5.3.2 Exclusion Criteria

1. Post-implant additional temporary or permanent mechanical circulatory support (MCS).
2. Post-implant Investigator mandated antiplatelet therapy for other conditions (including mandated presence or absence of antiplatelet agent).
3. Patients who are nil per os (NPO) post-implant through day 7.
4. Subjects with a known allergy to acetylsalicylic acid (aspirin).
5. Participation in any other clinical investigation(s) involving an MCS device, or interventional investigation(s) likely to confound study results or affect study outcome.
6. Presence of other anatomic or comorbid conditions, or other medical, social, or psychological conditions that, in the investigator's opinion, could limit the subject's ability to participate in the clinical investigation or to comply with follow-up requirements, or impact the scientific soundness of the clinical investigation results.

5.4 Subject Enrollment

Once informed consent is obtained, subjects are considered enrolled. Subject data entry into the EDC will begin following enrollment into the clinical investigation. Subject data will be collected following enrollment to the clinical investigation until the subject is withdrawn, experiences an outcome (transplant, explant, exchange, or death), or completes study follow-up.

Subjects who provide informed consent and are subsequently found to not meet inclusion/exclusion criteria prior to randomization or otherwise do not proceed to randomization will be withdrawn in accordance with section 5.5 of this CIP. Subjects who experience a surgical adverse event prior to day 14 that requires investigator mandated antiplatelet therapy (either presence or absence) will be withdrawn and not included in the analysis population. Subjects who expire prior to day 14 will not be included in the analysis population. All patients considered for this study, including enrolled subjects not included in the analysis population, will be reported in the study consort diagram.

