2.4.3 Treatment Arm Bottle Dispensing

Initial dispensing of the treatment arm bottle will occur upon randomization. Subjects will begin taking the treatment arm medication within 24 hours of randomization. Subjects will be resupplied 1 bottle at Month 3, Month 6, and Month 9 follow-up visits and 2 bottles at month 12 and every 6 months thereafter until study closure.

[REDACTED]

[REDACTED]

[REDACTED]

Subjects should always be sufficiently supplied with treatment arm medication until their next resupply visit. Each bottle will contain 120 capsules of the treatment arm medication, which is a sufficient supply for the period leading up to the subject's next visit, including the acceptable visit windows. Sites should carefully schedule follow up visits to ensure subjects are always sufficiently supplied.

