5.5 Subject Withdrawal

If a subject does not meet all inclusion criteria, or meets at least one exclusion criteria after the subject is enrolled (consented), but prior to randomization, the subject will be considered a screen failure and withdrawn and will not be included in the analysis populations.

Those enrolled (consented) subjects that meet all inclusion criteria and no exclusion criteria post implant will be randomized within 2-7 days post-implant (the day of implant is day 0). However, if these subjects do not meet the randomization eligibility criteria, are not randomized, never start the treatment arm regimen, experience a surgical event (≤ 14 days post implant) that requires investigator mandated anti-platelet therapy or experience an outcome ≤ 14 days post implant then they will be withdrawn.

Each randomized subject shall remain in the clinical investigation until completion of the required follow-up period; however, a subject's participation in any clinical investigation is voluntary and the subject has the right to withdraw at any time without penalty or loss of benefit. Conceivable reasons for discontinuation may include, but not be limited to, the following:

- Subject outcome including death, transplant, or device explant or exchange
- Physician or subject voluntary withdrawal
- Subject lost-to follow-up as described below.

The Sponsor must be notified of the reason(s) for subject discontinuation. The site will provide this information to the Sponsor. Investigators must also report this to their respective IRB/EC as defined by their institution's procedure(s).

No additional follow-up will be required or data recorded from subjects once withdrawn from the clinical investigation, except for the reason and status at the time of withdrawal (deceased/alive). Subjects withdrawn from the study will cease treatment arm medication and be transitioned to an anticoagulation regimen in accordance with site standard of care by the investigator.

In case of subject withdrawal of consent, the site should make attempts to schedule the subject for a final clinical investigation visit. At this final follow-up visit, the following will be recorded, with the subject's permission:

- Subject status (deceased/alive)
- Any adverse event details prior to withdrawal of consent

Lost-to-Follow-up

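### Randomised, dosed subjects withdrawn alive by day 14 leave the primary comparison, and their later endpoint status is never collected

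*Protocol*

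**What the plan says.** Timing. Under Protocol 5.5, eligible subjects "will be randomized within 2-7 days post-implant". Under 2.4.3, "Subjects will begin taking the treatment arm medication within 24 hours of randomization".

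Exclusion. Protocol 5.4: "Subjects who experience a surgical adverse event prior to day 14 that requires investigator mandated antiplatelet therapy (either presence or absence) will be withdrawn". The same sentence removes them from the analysis population, and the next adds: "Subjects who expire prior to day 14 will not be included in the analysis population". Section 5.1 builds the condition into the population itself: "Randomized subjects ongoing without a surgical adverse event, defined as ≤ 14 days post-implant, requiring investigator mandated antiplatelet therapy will form the analysis population". Section 5.5 lists among the grounds for withdrawal that subjects "experience a surgical event (≤ 14 days post implant) that requires investigator mandated anti-platelet therapy or experience an outcome ≤ 14 days post implant".

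Data after withdrawal. Section 5.5: "No additional follow-up will be required or data recorded from subjects once withdrawn from the clinical investigation", except the reason and the alive/deceased status at that time.

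Endpoint. Protocol 4.1: "Non-surgical is defined as any event occurring > 14-days post implant". SAP 2.3.1 makes mITT the primary analysis set. It counts death before the 12-month visit as failure. A subject with another outcome, such as transplant or explant for recovery, and no earlier non-surgical event counts as a success.

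Other relevant text. Protocol 5.6, which has no day-14 lower limit, keeps subjects with a mandated antiplatelet change in the study to month 12 where possible. SAP 2.10 summarises adverse events of subjects with surgical events up to day 14 apart from the two arms. The detailed mITT and ITT definitions, the analysis methods and the missing-data rules are redacted.

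**The concern.** Membership of the primary comparison is settled after randomisation and after dosing, by events that aspirin or its absence could plausibly affect. Blinding prevents a mandate from following known assignment. It does not prevent exclusions that result from a treatment effect.

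Three groups are removed by day 14, and two of them can be restored. Early deaths are failures under SAP 2.3.1, and transplant or explant for recovery without a prior event is a success. Subjects withdrawn alive after a surgical event cannot be restored. Their early event is not a primary failure, because only events after day 14 count, and whether they fail later is never recorded. No later analysis can recover that.

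There is also a scoring ambiguity. SAP 1.3 lists withdrawal among the study outcomes, and SAP 2.3.1 scores an outcome without a prior non-surgical event as success. On one literal reading, an ITT analysis would count these subjects as successes.

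**Working it through.** **What the plan gives.** 628 randomised (Protocol 5.7), 1:1 (Protocol 3.0), so 628/2 = 314 per arm. The margin is 10 points on a one-sided 97.5% limit (Appendix VIII). No rate of early mandated events is visible, so there is no figure of the plan's own to reproduce on this point. Its power and success-rate assumptions are redacted; 628 is used here only as the randomised total.

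**Exposure before the cut.** Randomisation on day 2-7 and a first capsule within one day put the start on day 2-8. By day 14 that is 14 - 8 = 6 to 14 - 2 = 12 days.

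**Assumptions.** mITT success p = 60%, 65% or 70% in both arms; observed mITT difference 0; k net placebo exclusions; later failure risk q among the excluded (q = 1 for deaths).

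**Formulas.**
- Placebo all-randomised success: pP = [p(314 - k) + (1 - q)k]/314. Aspirin: pA = p.
- Shift = k(1 - q - p)/314.
- Lower limit = (pP - pA) - 1.96·sqrt[pP(1 - pP)/314 + pA(1 - pA)/314]. Non-inferiority is lost at -10 points or below.
- With k = 0 the lower limit is -7.7, -7.5 and -7.2 points at p = 60%, 65% and 70%.

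**Shift in the risk difference (points).**

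| Case | p = 60% | p = 65% | p = 70% |
|---|---|---|---|
| k = 5, q = 0.6 | -0.32 | -0.40 | -0.48 |
| k = 10, q = 0.6 | -0.64 | -0.80 | -0.96 |
| k = 10, all scored as success | +1.27 | +1.11 | +0.96 |
| k = 5, deaths (q = 1) | -0.96 | -1.04 | -1.11 |

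Example: 10 × (1 - 0.6 - 0.6)/314 = -0.64 points. The gap between scoring 10 subjects as successes and a true 60% failure risk is 10 × 0.6/314 = 1.91 points.

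**Net placebo exclusions needed to lose non-inferiority.**

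| q | p = 60% | p = 65% | p = 70% |
|---|---|---|---|
| 0.5 | 73 | 52 | 44 |
| 0.6 | 37 | 32 | 29 |
| 0.8 | 19 | 18 | 18 |
| 1 (deaths) | 13 | 12 | 13 |

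At q = 0.6 that is 29/314 = 9% to 37/314 = 12% of an arm.

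**Equal counts do not settle it.** With 10 excluded per arm and later failure of 60% on placebo and 40% on aspirin, the shift is -10 × (0.6 - 0.4)/314 = -0.64 points.

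**Extreme bounds.** If m subjects per arm have unknown status, and all fail in one arm while all succeed in the other, the shift is ±m/314. For assumed losses of 1%, 3%, 5% and 10% (m = 3, 9, 16, 31) this is ±1.0, ±2.9, ±5.1 and ±9.9 points.

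**Scale of early deaths.** The CE Mark trial in Protocol 1.1.1 had 92% six-month survival (interval 83-97%, 50 subjects), so 8% mortality. Spread evenly over 182.5 days, 6-12 days carry 8% × 6/182.5 = 0.26% to 8% × 12/182.5 = 0.53%, or 0.8 to 1.7 deaths per 314 (0.3 to 3.5 over the interval). Hazard soon after implant may be higher than an even spread implies.

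**The case against.** Day 14 is a disclosed landmark. Primary events count only after it, survival in SAP 2.3.2 starts there, and the exclusion is stated in three protocol sections, with excluded subjects shown in the CONSORT diagram. Protocol 1.1.2 and 4.1 explain the wish to keep antithrombotic changes from distorting the first event. Mandates are made blind, and both presence and absence trigger withdrawal. Bias needs the capsule to change who is excluded or how the excluded later fare, and the documents give no evidence of either. The DSMB sees unblinded data, and SAP 2.14 reports termination reasons and causes of death by arm.

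The redactions matter too. An ITT population exists but its definition is hidden. SAP 2.1 points towards including everyone implanted and randomised, whereas SAP 2.10 points the other way. An uncited SAP reference on equivalence with censored data suggests that a censoring method may sit in the redacted part. The scored-as-success reading is weak: the examples in SAP 2.3.1 are transplant and recovery, these subjects are outside the mITT set, and Appendix VIII counts only survival to 12 months without an event.

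Most of this stands as a limit on size and certainty. It does not answer the central point: a rule in redacted text could impute or bound month-12 status, but could not recover data that were never recorded. Counts by arm do not replace that status either.

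**Conclusion.** The concern holds as a low-cost improvement. On the visible text, randomised and dosed subjects withdrawn alive by day 14 leave the mITT comparison and their later endpoint status is lost. That mITT applies this exclusion is read from Protocol 5.1 and 5.4 together with SAP 2.3.1 and 2.10, since the definition itself is redacted.

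The direction cannot be told from the plan. Net aspirin exclusions would reverse the sign, and with net exclusions from one arm the shift is nil if the excluded share the prognosis of those who remain. Under the assumptions above, 5-10 net placebo exclusions matter by 0.3 to 1.0 point, so overturning the primary conclusion looks unlikely unless early withdrawals are far more numerous or far more lopsided than that. Reversal through deaths alone also looks unlikely, and deaths can be restored in any case. Success rates, later failure risks and exclusion counts are assumptions, not figures from the plan.

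**What to change.** 1. Amend the follow-up wording of Protocol 5.4 and 5.5 so that withdrawal from capsules for an event by day 14 does not end follow-up. Follow every randomised subject who still consents to month 12 on the existing visits. The rules for stopping capsules are not touched.
2. Keep mITT as primary. Unless the redacted text already does so, pre-specify a supporting analysis of all randomised subjects by assigned arm. Count death from randomisation as failure, keep the after-day-14 rule for hemocompatibility events, and give tipping-point bounds where status is unknown. State that withdrawal alive for an early event is not scored as a success under SAP 2.3.1.
3. In SAP 2.10, show adverse events of randomised subjects excluded by day 14 by arm and reason.
4. Reconcile the cut-off in Protocol 5.4 (before day 14) with 5.1 and 5.5 (day 14 included), and reconcile 5.4 and 5.5 with 5.6 for events between randomisation and day 14.

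The cost is an amendment to the follow-up wording of two protocol sections, one table split by arm and possibly one supporting analysis. Visits and CRFs already exist. A few more subjects would be followed, and the supporting analysis would be slightly noisier. For anyone already withdrawn, only bounds are possible.
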